6 TRIAL PROCEDURES

The trial procedures for subjects are shown in Table 1.

Trial Code: 000205

Trial Code: 000205

Date: 10 Dec 2015 E-Protocol Amendment-19588; Ver. 1.0 Supersedes: 28 October 2015

Page 29 of 69

Table 1 Trial Assessments

	Screening		Stim	ulation	Post Trigger	Oocyte retrieval	Transfer	Pregnancy monitoring				End EOT ¹
	Pre-treatment			Trigger	retrievar		β-hCG			Ongoing		
	<90 days before Visit 2	Day 1 (Cycle Day 2-3)	Day 6	Protocol stimulation monitoring, Ovidrel® hCG injection	Post-hCG dose	36 h (±2 h) after hCG	5 days after oocyte retrieval	10-14 days after blastocyst transfer		4-5 weeks after blastocyst transfer	8-9 weeks after blastocyst transfer	
Visit	Visit 1	Visit 2	Visit 3	Unscheduled	Visit 4	Visit 5	Visit 6	Visit 7a	Visit 7b	Visit 8	Visit 9	
Written informed consent	X											
Inclusion/exclusion criteria	X	X										
Demographics, medical/infertility history	X											
Physical examination, vital signs	X											X
Gynecological examination with Pap smear ²	X											
Pregnancy test	X	X						X	X^3			
Local laboratory (standard of care E2, P4, hCG, LH)		X	X	X	X^4							
Central laboratory (E2, P4, hCG, testosterone, androstenedione, DHEA, FSH, LH)		X ⁵	X	X ⁶	X ⁷							
Central laboratory (AMH, chemistry, hematology)	X											X^{11}
Screening laboratory	X^8											
Randomization, dispense IMP		X^9										
TVUS (study-specific)	X	X	X	X	X		X^{12}			X	X	
Oocyte retrieval						X						
Blastocyst transfer/freezing							X					
Drug accountability (IMP only)			X	X	X							X
Concomitant medications	X^{10}	X	X	X	X	X	X	X		X	X	X
Adverse events		X	X	X	X	X	X	X		X	X	X

Ferring Pharmaceuticals

CONFIDENTIAL

Trial Code: 000205

Date: 10 Dec 2015

E-Protocol Amendment-19588; Ver. 1.0

Supersedes: 28 October 2015

Page 30 of 69

- 1. EOT assessments will be performed at the subject's last scheduled visit or the following day or within 2 weeks after the last scheduled visit in the case of premature discontinuation from the study.
- 2. Pap smear if not done in the previous 24 months.
- 3. For subjects who have a positive serum β-hCG at visit 7a. If conflicting results are obtained in the first 2 tests (visits 7a & 7b), a third test will be performed 2 days after the second test.
- 4. Including hCG or LH (if leuprolide acetate is given) in the morning.
- 5. No hCG on Day 1 of stimulation.

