6.7 Visits 7, 8, and 9 - Pregnancy Monitoring

- Visit 7: All subjects will be required to return to the clinic approximately 10-14 days after blastocyst transfer for β-hCG assessment. If the first serum β-hCG is positive, a second confirmatory test will be performed approximately 2 days later. If the pregnancy test is negative, ENDOMETRIN[®] will be discontinued and EOT procedures completed. If conflicting results are obtained in the first 2 tests, a third test will be performed 2 days after the second test. If a positive β-hCG is confirmed, ENDOMETRIN [®] will continue up to 10 weeks from the time it was initiated until the EOT Visit.
- **Visit 8**: Subjects who are pregnant will return to the clinic 4-5 weeks after blastocyst transfer for clinical pregnancy assessment (TVUS showing at least 1 intrauterine gestational sac with fetal heartbeat).

Trial Code: 000205

Date: 10 Dec 2015

E-Protocol Amendment-19588; Ver. 1.0

Supersedes: 28 October 2015

Page 35 of 69

• **Visit 9:** Subjects with clinical pregnancy will return to the clinic 8-9 weeks after blastocyst transfer for assessment of ongoing pregnancy (presence of at least 1 intrauterine pregnancy with a viable fetus with a detectable fetal heartbeat).

An End of Trial (EOT) Visit will be scheduled or completed for non-pregnant subjects and the information will be documented in the eCRF.

Non-pregnant subjects: Subjects without 2 positive β -hCG tests, clinical pregnancy, or ongoing pregnancy in the fresh cycle, may undergo a single frozen blastocyst transfer within 6 months of each subject's date of randomization. The PGS results can be used to select the euploid blastocyst for frozen transfer. Frozen-thawed blastocyst transfer cycle data will be collected, including blastocyst transfer information (endometrial thickness and echogenicity, grade of blastocyst, ploidy of blastocyst, presence of blood, or mucus within catheter tip), β -hCG serum results, clinical pregnancy, and ongoing pregnancy for the first frozen blastocyst transfer cycle following negative pregnancy.

Subjects may also return to the study center for regularly scheduled clinic visits as required per study center standard of care. The data collected during these visits will not be documented in the eCRF unless it is new or is a change in concomitant medications, pregnancy, or AEs.

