6.8 End of Trial (EOT) Visit

EOT assessments will be performed at the subject's last scheduled visit. If the EOT visit cannot be scheduled on the same day as the last scheduled visit, it can be done the following day. In the case of premature discontinuation from the study, an EOT visit will be completed within 2 weeks after the subject's last scheduled visit.

A physical examination will be done and vital signs will be recorded. The following laboratory tests will be performed by a central laboratory (no AMH will be drawn):

- Serum chemistry: non-fasting glucose, blood urea nitrogen, creatinine, potassium, sodium, chloride, calcium, aspartate aminotransferase, alanine aminotransferase, and gamma-glutamyl transferase.
- Hematology: red blood cell count, white blood cell count, hematocrit, hemoglobin, platelet count, and differential count.

Adverse events and concomitant medications will be assessed and documented and drug accountability will be performed.

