8.3 Pregnancy and Pregnancy Outcome

Subjects who achieve pregnancy (2 positive β -hCG tests) will be followed for clinical pregnancy (intrauterine gestational sac and/or fetal heart movement approximately 4-5 weeks after embryo transfer) and ongoing pregnancy (approximately 8-9 weeks after embryo transfer). Pregnant subjects will complete their final study visit approximately 8-9 weeks after embryo transfer (or sooner, if there is a loss of pregnancy). Subjects with ongoing pregnancy will be followed by telephone or mail for live birth data and information will be recorded in the eCRF. Pregnancy loss will be recorded on a pregnancy follow-up form in the eCRF.

Trial Code: 000205 Date: 10 Dec 2015 E-Protocol Amendment-19588; Ver. 1.0

Supersedes: 28 October 2015 Page 47 of 69

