9.8.2 Adverse Events

Adverse events will be coded using MedDRA.

A treatment-emergent AE is defined as an AE that emerges during treatment having been absent pre-treatment, or worsens relative to the pre-treatment state. Only treatment-emergent AEs will be presented in summary tables.

All data will be listed per subject and AE.

Written narratives will be issued for all SAEs and AEs leading to withdrawal. If causality is missing, the AE will be regarded as being reasonably possibly related to IMP. Related AEs (judged as being reasonably possibly related to IMP) will be termed adverse drug reactions.

Overview of Treatment Emergent Adverse Events

A treatment-emergent AE summary table will be presented, including for each treatment, the number of subjects reporting an AE, the percentage of subjects with an AE, and the number of events reported, for the following categories:

- All AE.
- Severe AEs
- Adverse drug reactions.
- AEs leading to discontinuation.
- SAEs.
- Deaths.

Incidence of Adverse Events

Treatment-emergent AEs in each treatment group will be tabulated by system organ class (SOC) and preferred term. The following will be presented: number of subjects reporting an AE, the percentage of subjects with an AE, and the number of events reported.

For each treatment the following counts are done:

- For number of subjects experiencing a particular event, counting will be done by subject and not by event. This is valid for both the SOC and preferred term, i.e., a subject will only be counted once in each SOC and once within each preferred term.
- For total number of events counting will be done by event. This is valid for both the SOC and preferred term, i.e., an event occurring more than once for the same subject will be counted for each occurrence.

E-Protocol Amendment-19588; Ver. 1.0 Supersedes: 28 October 2015 Page 56 of 69

Date: 10 Dec 2015

This counting and data presentation will be applied for the various incidences of AE tables described below.

Incidence of OHSS

OHSS for each treatment group will be tabulated by classification (mild, moderate, severe) and grade (1, 2, 3, 4, 5). The tabulation will be made for OHSS overall as well as separately for early OHSS and late OHSS.

Incidence of AEs by Relationship to IMP

Treatment-emergent AEs for each treatment group will be tabulated by SOC, preferred term, and relationship to IMP. One summary table will be prepared per type of relationship (related/not related).

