10.2 Adverse Events

Adverse events will be recorded from signed informed consent until the end-of-trial visit.

Adverse events (AEs) are classified according to the Medical Dictionary for Regulatory Activities (MedDRA) version 19.1 or later.

Missing values will be treated as missing, except for causality, intensity, seriousness, and outcome of AE. A ‘worst case’ approach will be used:

- if causality is missing, the AE will be regarded as related to the IMP
- if the intensity of an AE is missing, the AE will be regarded as severe
- if seriousness is missing, the AE will be regarded as serious
- if outcome is missing and no date of outcome is present, the outcome is regarded as ‘Not yet recovered’

Missing event start and event stop dates will be imputed in the most conservative way, i.e. the event should start as early as possible based on the (partially) missing start date while remaining treatment emergent (if relevant), and last as long as possible, i.e. until last visit or one day prior to the next event with the same preferred term, if any. In the latter case both consecutive AEs (with the same PT) will remain to be regarded as two separate events (despite being adjacent).

A treatment emergent adverse event is any adverse event occurring in the period from first administration of IMP till end-of-trial visit.

Pre-treatment adverse events will be reported in a listing only. This listing will be sorted by center and subject ID and date of onset.

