10.3 Chemistry and Hematology Laboratory Variables

Mean change and mean percentage (%) change from baseline at the end of trial will be presented for each laboratory variable. In addition, descriptive statistics, i.e., the number of subjects with data, mean, standard deviation, median, minimum, and maximum values, will be presented for observed values at screening and end of treatment for each laboratory variable.

Data listings will also be prepared by center for all subjects with any markedly abnormal laboratory safety values at any time-point (including screening/baseline) (appendix 1).

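### Treatment-emergent AEs and laboratory change run to an End of Trial visit whose date depends on outcome, so crude safety summaries can differ between arms without a drug effect if pregnancy or freeze-all rates differ

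*SAP*

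**What the plan says.** SAP 10.2 defines the counting window: "A treatment emergent adverse event is any adverse event occurring in the period from first administration of IMP till end-of-trial visit". Protocol 9.8.2 words it differently: "A treatment-emergent AE is defined as an AE that emerges during treatment having been absent pre-treatment, or worsens relative to the pre-treatment state". SAP section 12, which lists departures from the protocol analysis, does not mention the difference.

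The End of Trial (EOT) visit is tied to each subject's own course. Protocol 6.8 states: "EOT assessments will be performed at the subject's last scheduled visit". In practice:

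- **Excessive response, freeze-all (protocol 6.4):** EOT is scheduled or completed after retrieval and blastocyst evaluation, with no exact day.
- **Negative test (protocol 6.7):** Visit 7 is 10-14 days after transfer. Progesterone then "will be discontinued and EOT procedures completed".
- **Ongoing pregnancy (protocol 8.3):** the final visit is 8-9 weeks after transfer, or sooner if the pregnancy is lost.

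AEs are reported as subjects, percentages and event counts (SAP 10.2.1 and 10.2.2). The denominator is all subjects in the arm's safety set (protocol 9.8.1). For laboratory tests, SAP 10.3 says: "Mean change and mean percentage (%) change from baseline at the end of trial will be presented for each laboratory variable". No person-time rate, common observation window, or split by pregnancy or freeze-all status is planned for either. The early/late OHSS split in SAP 10.5.1 is the only safety summary anchored in time.

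**The concern.** Evaluating the AE profile of each drug is a stated secondary objective. A crude percentage of subjects with an AE depends on how long subjects are watched, and here that depends on whether the fresh cycle led to a pregnancy or was converted to freeze-all. Both follow randomization and either could differ by arm. The arm with more fresh-cycle pregnancies and fewer freeze-all cycles would accumulate more AE time, and could show more AEs even if the two gonadotropins were equally well tolerated.

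The laboratory summary has a related problem. One pooled mean change mixes women at 10-11 weeks' gestation with women days to weeks after trigger, so the mix can move the arm mean.

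Imbalance is plausible. Protocol 1.1 cites earlier high-AMH data with live birth of 34% versus 22% and high response of 32% versus 49% (MENOPUR versus rFSH), and this trial keeps a superiority option. High response there meant at least 15 oocytes, which is not this trial's freeze-all criterion, so the second figure is only indirect support.

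**Working it through.** The plan gives no length for the safety observation period, so there is no plan figure to reproduce on this point. The planning input that bears on it is the 50% ongoing pregnancy rate assumed in both arms (protocol 9.1).

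**Inputs**

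- Stimulation length S: at most 20 days (protocol 3.1.2). No expected length is given; assumed range 6-20, with 10 for illustration.
- Trigger to retrieval: about 36 hours, counted as 2 calendar days.
- Retrieval to transfer: 5 days. Blastocyst evaluation may extend to Day 7.
- Visit 7: transfer + 10 to 14 days. Visit 9: transfer + 56 to 63 days.

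**Step 1: days from first dose to EOT**

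Transfer = S + 2 + 5. Negative test = S + 7 + (10 to 14). Ongoing pregnancy = S + 7 + (56 to 63). Freeze-all at blastocyst evaluation = S + 7 to S + 9.

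| S | Negative test | Ongoing pregnancy | Freeze-all | Ongoing / negative | Ongoing / freeze-all |
|---|---|---|---|---|---|
| 6 | 23-27 | 69-76 | 13-15 | 2.6-3.3 | 4.6-5.8 |
| 10 | 27-31 | 73-80 | 17-19 | 2.4-3.0 | 3.8-4.7 |
| 20 | 37-41 | 83-90 | 27-29 | 2.0-2.4 | 2.9-3.3 |

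Each ratio runs from shortest over longest to longest over shortest; at S = 6, 69/27 = 2.6 and 76/23 = 3.3. If a freeze-all EOT came 14 days later, the last column would fall to 2.2-2.6 at S = 10.

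**Step 2: effect on arm means (S = 10, midpoints 76.5 and 29 days)**

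Take 50% versus 38% ongoing pregnancy (a 12-point difference), no freeze-all, and everyone else with a negative test:

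- 0.50 × 76.5 + 0.50 × 29 = 52.8 days
- 0.38 × 76.5 + 0.62 × 29 = 47.1 days

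The difference is 0.12 × 47.5 = 5.7 days. With 50% in both arms it is 0.

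**Step 3: illustrative effect on percentages**

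Let the percentage with an AE be the sum over groups of share × (1 − exp(−hazard × days)). Assume the same constant hazard of 0.01 per day in both arms and windows of 76.5, 29 and 17 days. The group values are 53.5% (ongoing), 25.2% (negative) and 15.6% (freeze-all).

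- Arm with 50% ongoing, 10% freeze-all, 40% negative: 38.4% (mean 51.6 days)
- Arm with 40% ongoing, 25% freeze-all, 35% negative: 34.1% (mean 45.0 days)

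The gap is 4.3 points with no drug effect. Now cluster the AEs around stimulation, with an assumed hazard of 0.02 per day to day 17 and 0.003 afterwards. The group values become 40.5%, 31.3% and 28.8%, the arms 35.6% and 34.4%, and the gap 1.3 points.

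**Step 4: end of a common period relative to OHSS**

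Day 5 after retrieval is about 1.5 + 5 = 6.5 days after trigger. Early OHSS runs to 9 days after trigger and late OHSS starts after that (protocol 7.1.6). A table ending at Day 5 would miss part of early OHSS and all late OHSS.

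**The case against.** The strongest reply is that nothing formal is at risk. Protocol 9.8.1 limits safety to summary tables and listings, so no AE test, interval or decision rule exists to be biased. Counting everything from first dose to trial end is a legitimate total-effect summary, and longer observation because a treatment worked is part of that effect. This stands: the problem arises only when the table is read as gonadotropin tolerability.

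Existing outputs also help: AEs by causality, SOC and preferred term, listings with onset dates, the early/late OHSS table and the excessive-response table. They aid interpretation, but none adjusts for observation time.

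On the definition, the protocol's wording gives no end date, protocol 8.2.1 already collects AEs to EOT, and trial-supplied progesterone continues in pregnant women (protocol 6.7). The SAP may simply be supplying a missing end point. Protocol section 9 also allows deviations to be described in the final report. What remains is that the two wordings differ and SAP section 12 is silent.

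A reader might infer that the AE comparison will be distorted by about 4 points. The documents do not support that. The figure needs assumed hazards and two assumed imbalances acting in the same direction, whereas the plan assumes equal pregnancy rates. At 300 per arm, 4.3 points is about 1.1 standard errors (SE about 3.9 points). Nor do the documents show that the later AEs are mainly first-trimester symptoms.

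**Conclusion.** The point holds as a limit on interpretation. Observation time depends on outcome: about 2.0-3.3 times as long in ongoing pregnancy as after a negative test, and about 2.9-5.8 times as long as in freeze-all women whose EOT is at blastocyst evaluation. Both ranges rest on the assumed 6-20 days of stimulation, and the second shrinks if the freeze-all EOT is later. They describe women who reach Visit 9; a pregnancy loss ends observation sooner.

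Crude AE percentages and the pooled laboratory change can then differ between arms without a drug effect, but only if pregnancy or freeze-all rates differ. The 1.3- and 4.3-point gaps are illustrations, not predictions. No size can be put on the laboratory effect from the documents.

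A reader might go further and conclude that the safety analysis is biased, or that a stimulation-period table should become the lead comparison. Neither follows. The tables are descriptive, and a lead table ending on Day 5 after retrieval would truncate OHSS in a high-responder trial.

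**What to change.** 1. **SAP 10.2:** keep the whole-trial table. Beside it, not in its place, add a TEAE table for the period observed in both arms whatever the later outcome: first IMP dose through Day 5 after retrieval, or cancellation. Also add event rates per person-time to EOT. The rates adjust for length of observation, not for differences between a stimulation week and a pregnancy week, so the two additions complement each other.
2. **SAP 10.5.1:** leave the OHSS tables untruncated, with early and late OHSS reported in full.
3. **SAP 10.3:** also show EOT laboratory values and changes by pregnancy status at EOT, labelled descriptive because they condition on post-randomization status.
4. **Definition:** reconcile the treatment-emergent wording in protocol 9.8.2 and SAP 10.2, and list the change in SAP section 12.

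Onset dates, visit dates and pregnancy status are already collected, and the primary analysis is untouched. The cost is SAP wording and a few more tables.

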8 ADVERSE EVENTS

8.1 Adverse Event Definition

An AE is any untoward medical occurrence in a subject participating in a clinical trial. It includes:

Trial Code: 000205

- Any unfavorable and unintended sign, symptom, or disease temporally associated with the use of the IMP, whether or not considered to be caused by the IMP.
- AEs commonly observed and AEs anticipated based on the pharmacological effect of the IMP.
- Any laboratory abnormality, vital sign, or finding from physical or gynecological examination assessed as clinically significant by the Investigator (findings from assessments and examinations done during screening are not AEs, but are recorded as medical history).
- Accidental injuries, reasons for any change in medication (drug and/or dose), reasons for any medical, nursing, or pharmacy consultation, or reasons for admission to hospital or surgical procedures.
- Overdoses and medication errors with and without clinical consequences.

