8.2.2 Recording of Adverse Events

The Investigator must record all AEs in the AE Log provided in each subject's eCRF with information about:

- AE description.
- Date and time of onset (time can be omitted, if not applicable).
- Intensity.
- Causal relationship to IMP.

Trial Code: 000205

Date: 10 Dec 2015

E-Protocol Amendment-19588; Ver. 1.0

Supersedes: 28 October 2015

Page 44 of 69

- Action taken to IMP.
- Other action taken.
- Date and time of outcome (time can be omitted, if not applicable).
- Outcome.
- Seriousness.

Each of the items in the AE Log is described in detail in the following sections.

Adverse Event

Adverse events should be recorded as diagnoses, if available. If not, separate signs and symptoms should be recorded. One diagnosis/symptom should be entered per record.

If a subject suffers from the same AE more than once and the subject recovers in between the events, the AEs should be recorded separately. If an AE changes in intensity, a worst-case approach should be used when recording the event, i.e., the highest intensity and the longest duration of the event.^a

Note the following: a procedure is not an AE; the reason for conducting the procedure is. Hospitalization is not an AE; the reason for hospitalization is. Death is not an AE, but the cause of death is (an exception is sudden death of unknown cause, which is an AE).

Date and Time of Onset

The date of onset is the date when the first sign(s) or symptom(s) were first noted. If the AE is an abnormal clinically significant laboratory test or outcome of an examination, the onset date is the date the sample was taken or the examination was performed.

Intensity

The intensity of an AE must be classified using the following 3-point scale:

Mild: Awareness of signs or symptoms, but no disruption of usual activity.

Moderate: Event sufficient to affect usual activity (disturbing).

Severe: Inability to work or perform usual activities (unacceptable).

Exception: if an AE with onset before the first IMP administration (i.e., a pre-treatment AE) changes in intensity, this must be recorded as 2 separate events. The initial AE should be recorded with outcome "not yet recovered" and the date and time of outcome is when the intensity changed. The second AE should be recorded with date and time of onset when the intensity changed.

Trial Code: 000205

Date: 10 Dec 2015 E-Protocol Amendment-19588; Ver. 1.0 Supersedes: 28 October 2015 Page 45 of 69

Causal Relationship to IMP

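### SAP 10.2 counts a pre-treatment adverse event that eases after first dose as treatment-emergent; Protocol 9.8.2 does not, and SAP 12 does not declare the difference

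*SAP*

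**What the plan says.** The two documents define a treatment-emergent AE differently.

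- Protocol 9.8.2: "A treatment-emergent AE is defined as an AE that emerges during treatment having been absent pre-treatment, or worsens relative to the pre-treatment state". The same section restricts the AE summary tables to such events.
- SAP 10.2: "A treatment emergent adverse event is any adverse event occurring in the period from first administration of IMP till end-of-trial visit". There is no comparison with the state before treatment. SAP 10.2 also confines pre-treatment events to a listing.

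Protocol 8.2.2 sets out how changes in intensity are recorded. The general rule is a single record: "If an AE changes in intensity, a worst-case approach should be used when recording the event". Pre-treatment events fall under an exception, which reads: "if an AE with onset before the first IMP administration (i.e., a pre-treatment AE) changes in intensity, this must be recorded as 2 separate events". Onset is then dated by a further sentence: "The second AE should be recorded with date and time of onset when the intensity changed". The exception does not distinguish worsening from improvement.

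Pre-treatment records can exist, because SAP 10.2 says "Adverse events will be recorded from signed informed consent until the end-of-trial visit". Their number is limited by Protocol 8.1, under which "findings from assessments and examinations done during screening are not AEs, but are recorded as medical history".

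SAP 12 lists departures from the protocol analysis: the dropped baseline summaries on the safety set, the dropped intention-to-treat sensitivity analysis, the added genetic-testing subgroup, and the wider window for the primary endpoint. The treatment-emergent definition is not among them.

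**The concern.** A rule based on onset date is a common shorthand for new-or-worse, and in many trials the two give the same tables. Here they do not, because the protocol's recording exception creates a fresh onset date for an event that has merely eased. The SAP has no rule that ties the second record to its pre-treatment parent or compares their intensities, so nothing in the plan removes it.

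The treatment-emergent flag decides what enters the overview table (SAP 10.2.1) and the tables by system organ class, preferred term, causality and intensity (SAP 10.2.2). An eased event would add a subject and an event to those tables, at the lower intensity. A programmer who followed the protocol would leave it out, so the same database could give two different sets of counts.

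**Working it through.** No figure in the plan is at issue, so there is nothing to recompute. The check applies both definitions to each kind of record that Protocol 8.2.2 can produce. A pre-treatment event is taken, as in that section, to be one with onset before first dose of investigational product.

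| Case | Records created | Protocol 9.8.2 | SAP 10.2 |
|---|---|---|---|
| 1. New event after first dose | One, post-dose onset | Emergent | Emergent |
| 2. Pre-treatment mild event becomes severe after first dose | Two; second has post-dose onset | Emergent (worse) | Emergent |
| 3. Pre-treatment severe event becomes mild after first dose | Two; second has post-dose onset | Not emergent (neither new nor worse) | Emergent |
| 4. Pre-treatment event changes intensity before first dose | Two, both pre-dose onset | Not emergent | Not emergent (listing) |
| 5. Pre-treatment event continues unchanged | One, pre-dose onset | Not emergent | Not emergent (listing) |

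The definitions part only in case 3.

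- **Case 2.** Leaving worsening out of the SAP sentence loses nothing, because the split gives the worsened event its own post-dose onset.
- **Case 3.** The second record's onset lies inside the SAP window. By that onset it is no longer a pre-treatment event, so the listing-only sentence does not catch it. The result is the same whether the SAP's word for occurrence means onset or presence.
- **Case 5.** The SAP definition taken alone could include an event that is still present. Read with the listing-only sentence and the protocol's meaning of pre-treatment, it does not.

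To fall into case 3, an event must start after consent, not be a finding from a screening assessment or examination, be moderate or severe, persist past first dose, and then ease without resolving. The documents give no number for any of these steps, so the size of the set cannot be calculated.

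**The case against.** The strongest reply is that the SAP errs only towards inclusion. No worsening is lost, the record type is narrow, and Protocol 9.8.1 plans only tables and listings for safety, with no formal comparison. All of that stands, and it keeps the point small. It does not remove the mismatch: the SAP tabulates a record that the protocol's own definition excludes.

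It can also be said that Protocol section 9 allows departures to be described in the SAP or the final report, and that SAP 10.2 states its definition openly. That is fair. But SAP 12 is the section set aside for such departures, and a reader of it would not learn that this definition had changed.

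A reader might infer four stronger things that the documents do not support.

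- **That every pre-treatment event still present at first dose is counted.** Unchanged events go to the listing (case 5).
- **That recoveries are counted as new events.** Recovery is an outcome code in Protocol 8.2.2, not a change of intensity. A resolved event is closed and creates no second record.
- **That arm differences are diluted or preferred terms pushed over the 5% cut-off.** With arms of equal size n, adding k subjects to each leaves the difference unchanged: (x1 + k)/n − (x2 + k)/n = (x1 − x2)/n. Only a ratio moves. If 1% of subjects had such an event, that would be 0.01 × 300 = 3 per arm, against a cut-off of 0.05 × 300 = 15. The 1% is hypothetical, and the comparison puts all such events in one preferred term.
- **That eased events would appear as drug reactions.** This needs the investigator to judge the milder event possibly caused by the product, or the causality field to be blank and imputed as related under SAP 10.2.

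**Conclusion.** The concern holds for one record type: a pre-treatment AE that steps down in intensity after first dose without resolving. SAP 10.2 counts it as treatment-emergent, Protocol 9.8.2 does not, and SAP 12 does not declare the change.

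The consequence is minor over-counting in descriptive safety tables. The primary analysis is unaffected. Two judgements on size are assumptions, not figures from the documents. The first is that such records are rare, which rests on screening findings going to medical history. The second is that the arms are affected alike. Protocol 4.2.2 places randomization immediately before dosing, so pre-treatment events should be balanced in expectation. How often they then ease is assumed not to differ by arm.

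**What to change.** Change the SAP 10.2 definition, keeping its end-of-trial limit. A treatment-emergent AE is then either:

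- an event with onset on or after first dose that was not present before treatment; or
- a re-entered pre-treatment event whose intensity is higher than that of its linked pre-treatment record.

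Keep re-entered records of lower or equal intensity in the pre-treatment listing. Equal intensity has to be named: an event that eases after dosing and later returns to its former level would be recorded at its highest intensity, which matches the parent record. The rule should also cover a parent record with missing intensity. The SAP imputes missing intensity as severe, and no re-entered record could then count as worse.

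If the sponsor prefers the wider definition, the alternative is to declare and justify it in SAP 12.

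The cost is one sentence and one programming flag. The downside is that the link between each re-entered record and its parent has to be checked at data review.
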